8.3.3. Prognostic Endpoints and Markers of Inflammation

Change and percentage change from Baseline for MELD score, MELD-Na score, Child-Pugh score, Mayo Risk Score (MRS), IgM, C-reactive protein (CRP), tumor necrosis factor- α (TNF- α), FGF-19, cytokeratin-18 (CK-18), C4, and enhanced liver fibrosis (ELF) score will be summarized and analyzed using the Wilcoxon Rank Sum Test to compare groups at annual timepoints. The median differences and 95% CI of the median differences between treatment groups will be constructed using Hodges-Lehmann estimate. If the median differences between treatments are not approximately symmetrical around the median, the Sign Test may be used.

Values below or above the quantifiable limits will be handled as follows. Quantitative laboratory tests containing less than (<) and greater than (>) symbols are test results that are below and above quantifiable limits, respectively. In order to retain these values for analysis purpose, the following imputations will be done within the analysis datasets:

For laboratory test results that are below the quantifiable limit:

$$\text{Imputed laboratory results} = (\text{numeric portion of the result}) \times 0.9.$$

For laboratory test results that are above the quantifiable limit:

$$\text{Imputed laboratory results} = (\text{numeric portion of the result}) \times 1.1$$

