3. SUMMARY OF STUDY DESIGN

[figure not shown]
This Phase 4, double-blind, randomized, placebo-control, multicenter study will evaluate the effect of OCA on clinical outcomes in subjects with PBC who are at higher risk of liver-related clinical complications.

Eligible subjects will have a diagnosis of PBC with bilirubin levels $>ULN$ and $\leq 5x ULN$ and/ or $ALP > 3x ULN$. Subjects will be screened twice during a 1- to 8-week Screening period prior to entering the study to allow for the collection of repeat serum chemistry samples (at least 2 weeks apart) to confirm pretreatment alkaline phosphatase (ALP) and total bilirubin values.

Investigational product (IP) will be taken orally, once daily for the majority of subjects; dose and frequency will be modified for subjects with cirrhosis (including subjects progressing to cirrhosis during the study) and classified as Child-Pugh B or C. The randomization will be stratified by ursodeoxycholic acid (UDCA) treatment (yes/ no) and baseline bilirubin categories ($>$ upper limit of normal [ULN]/ $\leq ULN$). A minimum of 30% of subjects will have elevated bilirubin ($>ULN$) at Screening.

The study is event driven and will continue until approximately 127 adjudicated primary endpoint events have been accrued in unique subjects, or until the Sponsor (eg, based on a recommendation from the Data Monitoring Committee (DMC)) terminates the study. Subjects are expected to be followed for a minimum of approximately 6 years. Figure 1 below displays the study design diagram. Schedules of study procedures are outlined in Table 1 (Screening to Month 12) and Table 2 (Year 2 to End-of-Study Endpoints) of the study protocol, where more details are provided.

Figure 1: Schematic Diagram Study 747-302

EOS = end of study; M = month, OCA = obeticholic acid; ULN = upper limit of normal
 Initial dose titration of investigational product should occur at the Month 3 visit, or any study visit thereafter for subjects on all dosing regimens, based on tolerability and biochemical response (Up-titration should be considered when ALP and/ or total bilirubin are $>ULN$). Subsequent dose titration(s) for subjects classified as Child Pugh B or Child-Pugh C and following a modified dosing schedule may occur no earlier than 6 weeks after the previous dose titration.

Dosing frequency will be determined by the presence or absence of cirrhosis and, if cirrhosis is present, by Child-Pugh Score as described below:

	Planned Dosing Regimen	

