All statistical tests comparing groups will be conducted at the 2-sided, 0.05 level of significance, unless otherwise specified (eg, the primary efficacy analysis, [Section 8.6](#)). Summary statistics for each treatment group will be presented, as well as 95% CIs comparing groups.

Baseline Definitions

The Baseline value for statistical analyses of quantitative parameters is defined as the mean of all available study evaluations after the subject signs the informed consent and prior to or on the first administration of investigational product, unless otherwise specified. If there is only one evaluation prior to the first administration of investigational product then the available data from this evaluation will be used as the Baseline value.

The baseline value for analyses of lipid parameters is defined as the last fasted evaluation prior to the first administration of IP.

The baseline value for analyses of qualitative parameters (eg, normal/abnormal) is defined as the last evaluation prior to the first administration of IP.

Baseline values defined above will not change regardless if a subject stops taking investigational product and begins taking commercially marketed OCA.

Visit Windows

Visit windows, as provided below, will be established relative to an individual’s Day 0, the date of first administration of investigational product. Analyses will use visit windows defined by relative day, overriding CRF designated visit numbers.

OCA Therapy 3-Month Interval Visit Windows (Days)

Months	Target Study Day ^a	Analysis Window Study Day ^a	
		Low	High
Day 0	1	Closest visit to Day 1, prior to first IP dose ^b	
Month 1	30	2	46
Month 3	90	47	137
Month 6	183	137	227
Month 9	274	228	318
Month 12	365	319	410
...
Month n^b	$\text{round}(365.25/12*n)$	$\text{round}(365.25/12*n) - 46$	$\text{round}(365.25/12*(n+3)) - 47$

Note: Follow-up visits are not included in visits windows.

^a Study day will be calculated from first dose date.

^b For n in three month increments (15, 18, 21, ...).

Partial Dates

If only a partial date is available and is required for calculation, the following standards will be applied:

- Diagnostic Date (eg, PBC diagnostic date)
 - For missing day only – Day will be imputed as the first day of the month (ie, 1).
 - For missing day and month – Day and month will be imputed as the first day of the year (ie, 1 January).
- Start Dates (eg, event date, AE onset date, or start date of medication)

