duration in years = $(date2 - date1 + 1)/365.25$, where $date1 \geq$ first dose date

duration in years = $(date2 - date1)/365.25$, where $date1 <$ first dose date

- Age – Age is calculated as the number of years from the date of birth (*DOB*) to the specified date, eg, date of informed consent (*DOIC*). If the month of *DOIC* < month of *DOB* or the month of *DOIC* = *DOB* and the day of *DOIC* < day of *DOB*, then the following formula is used:
$$\text{age (years)} = \text{year of DOIC} - \text{year of DOB} - 1.$$

Otherwise, the following formula is used:

$$\text{age (years)} = \text{year of DOIC} - \text{year of DOB}.$$

If only year is provided in *DOB*, then July 1 will be used for the month and day.
- Change from Baseline – Change from Baseline will be calculated as:
$$\text{Change} = \text{post Baseline value} - \text{Baseline value}$$
- Percentage change from Baseline – Change from Baseline will be calculated as:
$$\text{Percentage change from Baseline} = \frac{[\text{post Baseline value} - \text{Baseline value}]}{\text{Baseline value}} \times 100$$
- MELD score is derived using the following formula:
$$\text{MELD} = 3.78 \times \ln[\text{serum bilirubin (mg/dL)}] + 11.2 \times \ln[\text{INR}] + 9.57 \times \ln[\text{serum creatinine (mg/dL)}] + 6.43 \times \text{aetiology}(0: \text{cholestatic or alcoholic}, 1: \text{otherwise}).$$

Laboratory values less than 1.0 are set to 1.0 when computing the MELD score.
- MELD-Na score is derived using the following formula:
$$\text{MELD-Na} = \text{MELD} + 1.32 \times (137 - [\text{adjusted sodium (mmol/L)}]) - [0.033 \times \text{MELD} \times (137 - [\text{adjusted sodium (mmol/L)}])],$$

where adjusted sodium is equal to

 - $[\text{serum sodium (mmol/L)}] + 0.024 \times ([\text{serum glucose (mg/dL)}] - 100)$
when serum glucose > 100 mg/dL
 - $[\text{serum sodium (mmol/L)}]$
when serum glucose ≤ 100 mg/dL

and adjusted sodium values less than 125 mmol/L are set to 125, and values greater than 137 mmol/L are set to 137.
- Child Pugh classification (Noncirrhotic/A/B/C) is defined as follows: Subjects deemed noncirrhotic at baseline by the PI are captured as “noncirrhotic” regardless of baseline Child-Pugh score and those without a cirrhosis assessment or who were deemed cirrhotic at baseline are summarized by their baseline (Screening or Day 0) Child-Pugh category.
- Rotterdam Criteria (Mild/Moderate/Severe) is defined as follows:
Mild - Total Bilirubin ≤ ULN and Albumin ≥ LLN

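### Percentage change from baseline in MELD and MELD-Na is undefined at a baseline of 0, which the SAP's formulas allow in PBC, and unstable just above it

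*SAP*

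**What the plan says.** Section 8.3.3 of the SAP lists "Change and percentage change from Baseline for MELD score, MELD-Na score, Child-Pugh score" together with the Mayo Risk Score and several inflammation and fibrosis markers. Both forms of change are to be summarised and compared between arms by the Wilcoxon rank sum test at annual timepoints, with Hodges-Lehmann estimates of the median difference. Section 8.7 repeats the section 8.3.3 endpoints in the baseline disease-stage subgroups.

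Appendix A, Standard Calculations, fixes the ingredients:

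- Percentage change is the post-baseline value minus the baseline value, divided by the baseline value, times 100 (under "Percentage change from Baseline – Change from Baseline will be calculated as").
- The MELD aetiology term is 0 for disease that is "cholestatic or alcoholic" and 1 otherwise.
- "Laboratory values less than 1.0 are set to 1.0 when computing the MELD score".
- For MELD-Na, adjusted sodium is bounded, and "values greater than 137 mmol/L are set to 137".

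Appendix A, Baseline Definitions, takes the quantitative baseline from pre-dose data: "defined as the mean of all available study evaluations after the subject signs the informed consent and prior to or on the first administration". No rule is given for a baseline of zero.

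Section 3 allows entry on raised bilirubin and/or on ALP above 3 times ULN, and states that "A minimum of 30% of subjects will have elevated bilirubin". Subjects with normal bilirubin are therefore part of the intended population.

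**The concern.** A percentage change needs a baseline that is clearly above zero. The MELD formula as coded has no constant for a PBC subject, and the floor at 1.0 turns each normal or low component into a zero term. The lowest possible score is exactly 0, and subjects with mild disease cluster at or near it.

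Two things follow:

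- **At 0**, the percentage is undefined. Those subjects drop out of the percentage analyses while remaining in the absolute-change analyses planned in the same sentence, so the two sets of results describe different subjects. The subjects lost are those with the lowest scores, who can only stay level or worsen.
- **Just above 0**, a trivial laboratory shift becomes a very large percentage. It takes an extreme rank in the Wilcoxon test and dominates any mean or SD of percentage change.

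Unless the SAP settles this, the handling falls to an unplanned programming decision.

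**Working it through.** The SAP states no MELD result to reproduce, so the check evaluates its own formulas directly.

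**Formulas (Appendix A, Standard Calculations)**

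- MELD = 3.78 ln(bilirubin, mg/dL) + 11.2 ln(INR) + 9.57 ln(creatinine, mg/dL) + 6.43 × aetiology, with each laboratory value below 1.0 set to 1.0. For PBC the last term is 6.43 × 0 = 0.
- MELD-Na = MELD + 1.32 × (137 − Na) − 0.033 × MELD × (137 − Na), with adjusted sodium held between 125 and 137.
- Percentage change = (post − baseline) / baseline × 100.

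The laboratory values below are illustrative assumptions, because the SAP gives no baseline distribution.

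**Step 1: the zero baseline.** Take bilirubin 0.6, INR 1.0, creatinine 0.8, sodium 140. After flooring, every component is 1.0 and ln(1) = 0, so MELD = 0. Sodium is capped at 137, so 137 − Na = 0 and MELD-Na = 0. Percentage change has a zero denominator.

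MELD-Na reaches 0 less often than MELD. With MELD = 0, it is 1.32 × 1 = 1.32 at sodium 136 and 1.32 × 2 = 2.64 at sodium 135.

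**Step 2: just above the floor.** With bilirubin and creatinine at or below 1.0:

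| INR, baseline to follow-up | MELD | Absolute change | Percentage change |
|---|---|---|---|
| 1.02 to 1.10 | 0.22 to 1.07 | +0.85 | +381% |
| 1.05 to 1.15 | 0.55 to 1.57 | +1.02 | +186% |

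The terms are 11.2 ln(1.02) = 0.22, 11.2 ln(1.05) = 0.55, 11.2 ln(1.10) = 1.07 and 11.2 ln(1.15) = 1.57. Percentages use unrounded scores.

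**Step 3: the same 1-point rise from different baselines** (components not listed are at or below 1.0).

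| Baseline values | MELD | +1 point as a percentage |
|---|---|---|
| bilirubin 1.02 | 0.075 | 1336% |
| bilirubin 1.05 | 0.184 | 542% |
| INR 1.05 | 0.546 | 183% |
| INR 1.10 | 1.067 | 94% |
| bilirubin 3, INR 1.2 | 6.195 | 16% |

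The last row is 3.78 ln(3) + 11.2 ln(1.2) = 4.15 + 2.04 = 6.19.

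**Step 4: does averaging the baseline remove the problem?** Three pre-dose scores of 0, 0 and 1.067 average to 1.067 / 3 = 0.356. Averaging makes an exact 0 rarer, but the baseline stays close to it.

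**Step 5: does absolute change work?** A subject with baseline 0 who moves to bilirubin 1.2, INR 1.1, creatinine 0.8 changes by 3.78 ln(1.2) + 11.2 ln(1.1) = 0.69 + 1.07 = +1.76 points. This is defined for every subject with both values.

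**The case against.** The strongest reply is that little turns on this. These are additional secondary endpoints, outside the testing hierarchy and tested at nominal alpha (section 8.6). Absolute change sits beside the percentage, and setting an undefined percentage to missing is an ordinary programming convention. Rank methods also limit what a value of +381% can do. All of this stands, and it is why the point is minor. It does not make the measure usable: a rank test cannot rank an undefined value, and trivial shifts still take extreme ranks.

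A reader might infer more than the documents support in four ways:

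- **Bias between arms.** Exclusion depends only on a pre-treatment value, and the arms are randomised 1:1 within bilirubin strata (section 3.1). The remaining comparison is still randomised. What is lost is sample size and coverage of the mildest subjects.
- **Up to 70% of subjects affected.** That is the complement of the enrolment minimum for raised bilirubin, so it is a design ceiling for bilirubin at or below ULN. An exact 0 needs all three components at or below 1.0, and the SAP gives no bilirubin ULN in mg/dL.
- **Imputation adding zeros.** Table 1 sits under the primary endpoint in section 8.1 and is used only when no value exists in the preceding year. Only the baseline is a denominator, and subjects are screened twice, so its contribution is marginal.
- **Harm to the primary endpoint.** The MELD and MELD-Na events at 15 or above use the score itself and are untouched.

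**Conclusion.** The point holds as a minor one. As written, percentage change in MELD and MELD-Na is undefined for any subject whose baseline score is 0 and unstable for those just above it. Near the floor, shifts of about 1 point are worth anything from 94% to over 1300% in the examples, against 16% from a baseline of 6.19. The percentage and absolute analyses would run on different subjects, and means and SDs of percentage change would be driven by near-zero baselines.

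The conclusion rests only on the Appendix A formulas and on the fact that section 3 admits subjects with normal bilirubin on ALP alone. The INR, bilirubin and creatinine values used are assumptions for illustration. The number of subjects affected could be many or few and cannot be derived from the SAP.

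**What to change.** In section 8.3.3, delete percentage change for MELD and MELD-Na, and state that these two scores are analysed by absolute change only, for all subjects with baseline and follow-up values. The subgroup repeats in section 8.7 then follow automatically. Leave the other measures in that sentence as planned.

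The cost is one line of SAP wording and fewer outputs. The absolute-change analyses are already planned.

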3.1. Randomization and Blinding

This study will be conducted in a double-blind, placebo-controlled manner. Allocation to one of two treatment groups (OCA or placebo) will occur on a 1:1 ratio across sites and will be stratified by UDCA treatment (yes/no) and mean baseline bilirubin categories (>ULN/≤ULN), as specified by the central laboratory. The randomization will be based on a predefined randomization code (generated by the Sponsor or designee) using an interactive web response system (IWRS). The IWRS will also serve as an investigational product inventory and management system and may be integrated with the study database.

The unblinded data access during DMC and interim analysis is described in Safety Review Committee Charter.

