3.2. Sample Size Determination

The following assumptions were used in the Protocol Version 6 sample size calculations:

- Exponential survival curves, placebo survival estimate of 0.6 at 8 years with a hazard ratio of 0.60, and total study duration of 10 years (from first subject enrolled), allowing for 4 years of subject accrual and 6 years of follow up.
- Subjects will be randomized in a 1:1 ratio to placebo or OCA.
- The 2 treatment groups will be compared using a 2-sided log rank test at the 5% level of significance.
- Two interim analyses and one final analysis are planned, with interim analyses occurring after the accrual of 50% and 75% of clinical outcome events, respectively.
- A dropout rate of 10% is assumed

Based on the randomization ratio, significance level, and assumed hazard ratio, a total of 127 events (both groups combined) was to provide 80% power to demonstrate a statistically significant difference between OCA and placebo on time to liver-related outcomes, including all-cause mortality.

In addition, based on the remaining assumptions stated above, it was estimated that approximately 428 subjects would be enrolled to attain 127 events.

Sample size calculations were based on the following composite endpoint: time to first occurrence of death, liver transplant, MELD ≥ 15 , uncontrolled ascites, or hospitalization for new onset or recurrence of variceal bleed, hepatic encephalopathy, or spontaneous bacterial peritonitis.

Due to enrollment challenges and difficulties to keep patients in the study, the trial will be terminated early by sponsor. To better evaluate the benefit-risk ratio, the composite endpoint will be revised to include additional components that occur earlier in the progression of PBC

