8.3.2. Liver Biochemistry Analyses

Analyses of changes in liver biochemistry (gamma-glutamyl transferase (GGT), ALT, AST, conjugated bilirubin, albumin, and INR) at each visit will be compared between treatment groups using a restricted maximum likelihood based mixed-effect model repeated measures (MMRM) with treatment, baseline, visit, visit by treatment interaction and randomization stratification factors to be included in the model. Visits through Month 24 will be included. An unstructured covariance model will be used. If the computational algorithm fails to converge, the following structures will be tested in the order: Toeplitz, AR(1) and compound symmetry (CS). If the model still does not converge, the stratification factors will be dropped from the model one at a time (UDCA followed by bilirubin).

Change from Baseline over time will be analyzed using analysis of covariance (ANCOVA) with change from Baseline as the dependent variable including treatment group and randomization stratification factor as fixed effects and the Baseline values as a covariate. Descriptive statistics of the laboratory values will be summarized by treatment group. The results, change from

Baseline, and percentage change from Baseline values, as well as estimates of least-square means, standard errors, and 95% CIs, will be presented by treatment group. Estimates of the mean difference between treatment groups, the standard error of the difference, and 95% CI of the difference will be presented.

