8.6. Multiple Comparisons/Multiplicity

An interim analysis was conducted after 80 events were observed. A group sequential design using the O'Brien-Fleming type alpha-spending function ([Lan 1983](#), [Reboussin 2000](#)) was used to control the overall two-sided 0.05 significance level that is at an information fraction of 0.63 of the total of 127 events, corresponding to an alpha spend of 0.009. The primary analysis will be conducted at 2-sided 0.041 significance level. No interim analysis will be performed based on the updated endpoints and methodology. The primary endpoint analysis for European Medicines Agency (EMA) filing will be conducted at 2-sided 0.041 significance level.

For the final analysis, the hypothesis testing of key secondary analyses will compare placebo and OCA (the key secondary endpoints are stated in [Section 8.2](#)), provided that the primary efficacy endpoint comparison is statistically significant in favor of OCA. If the primary comparison is not statistically significant then comparison of the key secondary endpoints will be considered as supportive or supplemental. If the primary comparison is statistically significant, the key secondary endpoints will be tested hierarchically in the order described in [Section 8.2](#) at a 2-sided 0.041 significance level. All other secondary endpoints will be tested at nominal 0.041 alpha level.

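### Section 8.3.3 compares the prognostic scores and inflammation markers by an unstratified, baseline-unadjusted Wilcoxon test; a stratified rank ANCOVA would usually gain power from data already held

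*SAP*

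**What the plan says.** SAP section 8.3.3 covers MELD, MELD-Na, Child-Pugh, Mayo Risk Score, IgM, CRP, TNF-alpha, FGF-19, CK-18, C4 and ELF. Change and percentage change from baseline "will be summarized and analyzed using the Wilcoxon Rank Sum Test to compare groups at annual timepoints". The estimate is also unadjusted: "The median differences and 95% CI of the median differences between treatment groups will be constructed using Hodges-Lehmann estimate". The fallback adds neither term: "If the median differences between treatments are not approximately symmetrical around the median, the Sign Test may be used".

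Section 8.3.2, on liver biochemistry, uses an ANCOVA "including treatment group and randomization stratification factor as fixed effects and the Baseline values as a covariate", and its MMRM carries the same terms. Section 3.1 has allocation "stratified by UDCA treatment (yes/no) and mean baseline bilirubin categories". The same factors stratify the log rank test and Cox model (8.1.1) and the CMH tests (8.3.1, 8.4.2).

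On error rate, section 8.6 says "All other secondary endpoints will be tested at nominal 0.041 alpha level". The general rule in Appendix A ("All statistical tests comparing groups will be conducted at the 2-sided, 0.05 level of significance, unless otherwise specified") gives way to that, so 0.041 is used below.

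**The concern.** A rank sum test on change uses baseline only by subtracting it, or by dividing it out for percentage change. If the regression slope of follow-up on baseline is below 1, subtraction removes too much, and baseline variation left in the change score widens the comparison. A covariate term would remove it. The strata are left out as well, although by the Appendix A formula MELD contains the logarithm of bilirubin and MELD-Na is built on MELD. Those outcomes are therefore tied directly to a stratification factor.

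What is at stake is precision. Markers of inflammation and fibrosis belong to a stated secondary objective (2.1.2), and section 8.7 repeats the 8.3.3 analyses in the baseline disease-stage subgroups, where numbers are smaller. Section 8.3.3 gives no reason for dropping adjustments used elsewhere in the plan.

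**Working it through.** **Plan's own figure.** There is none to reproduce. The only sizing (127 events, about 428 subjects, section 3.2) is for the original composite endpoint. No power, effect size, SD or correlation is given for the 8.3.3 endpoints.

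**Inputs from the documents.** About 334 subjects enrolled (Clinical Pharmacology Analysis Plan, section 5); 1:1 allocation ("Subjects will be randomized in a 1:1 ratio to placebo or OCA", section 3.2); two-sided 0.041 (section 8.6). Fewer subjects will have data at later annual visits, so 334 is a ceiling.

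**Assumed.** rho from 0.3 to 0.9; k, the ratio of baseline SD to follow-up SD; the shape of the data; and an effect that gives the planned test about 75-77% power.

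**Step 1: variance.** For normal data, the variance of a baseline-adjusted comparison relative to a change-score comparison is

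(1 - rho²) / (1 + k² - 2·rho·k).

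With k = 1 this is (1 + rho)/2: 0.65, 0.75, 0.85, 0.90 and 0.95 at rho 0.3, 0.5, 0.7, 0.8 and 0.9.

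**Step 2: what that could buy at best.** Power of 76% at two-sided 0.041 needs a standardised effect of 2.044 + 0.706 = 2.750. Divide by the square root of the ratio, subtract 2.044 and convert to a probability:

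| rho | 2.750/√ratio | Power | Gain |
|---|---|---|---|
| 0.3 | 3.411 | 91% | 15 |
| 0.5 | 3.175 | 87% | 11 |
| 0.7 | 2.983 | 83% | 7 |
| 0.8 | 2.899 | 80% | 4 |
| 0.9 | 2.821 | 78% | 2 |

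**Step 3: what the stratified rank method delivers.** A rank method need not capture all of this. Simulation with 334 subjects, two-sided 0.041, normal data and k = 1, comparing the Wilcoxon test on change with stratified rank ANCOVA, gave gains of about 12, 10, 4, 2 and 0 points at the same five values of rho. The adjusted test held its size. A second simulation of the same comparison gave 13, 8, 5, 4 and 2 points (for example 78% to 91% at rho 0.3 and 77% to 82% at 0.7), with size 0.043 against 0.041.

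**Step 4: unequal SDs.** With k = 0.8:
- rho 0.7: ratio 0.51/0.52 = 0.98
- rho 0.8: ratio 0.36/0.36 = 1.00
- rho 0.9: ratio 0.19/0.20 = 0.95

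Almost nothing is left to gain. Simulation with 150 per arm agrees: 75.5% against 75.8% at rho 0.7, and 76.7% against 76.5% at rho 0.8. The worst simulated result for k = 0.8 and rho of 0.7 or more was a loss of about 2 points.

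**Step 5: skewed data.** On log-normal data, rank ANCOVA on change beat Wilcoxon on change at every rho tried, but the size depended on the set-up. With 167 per arm at two-sided 0.05 the gain ran from 67.6 - 48.9 = 18.7 points (rho 0.3) to 68.4 - 65.2 = 3.2 (rho 0.9). With 334 subjects at 0.041 it ran from about 10 points (rho 0.3) to about 1 (rho 0.9).

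**The case against.** The strongest objection is that the gain is not assured. It needs the slope, rho times follow-up SD over baseline SD, to be below 1, and the plan gives reasons to doubt equal SDs. Appendix A averages all pre-dose values for baseline, and entry caps bilirubin at 5 times ULN, while follow-up values can spread over years. This stands. A reader might infer that a change score over-corrects whenever rho is below 1; that is true only with equal SDs.

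Second, a rank test suits skewed markers such as CRP, TNF-alpha and IgM. This also stands, and it rules out raw-scale ANCOVA as a blanket replacement: on log-normal data at rho 0.7, raw-scale ANCOVA had 49.0% power against 57.8% for Wilcoxon on change. It does not count against a method that is itself rank-based.

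Third, Wilcoxon on percentage change reached 69.3% in that setting, against 66.6% for rank ANCOVA on change. That compares two different outcomes. The plan analyses both, so each should be adjusted and compared with its own unadjusted version; on that footing adjustment still gained on log-normal data.

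Fourth, little depends on these tests. They are nominal and outside the hierarchy. This stands and limits the weight of the point.

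**Conclusion.** The point holds as an efficiency improvement. Under the assumptions above (normal data, equal SDs, 334 subjects, two-sided 0.041) the planned test gives up about 12 points of power at rho 0.3, 10 at 0.5, 4 at 0.7, 2 at 0.8 and about none at 0.9, from a starting power of about 75-77%. With follow-up clearly more variable than baseline and rho of 0.7 or more, there is little or nothing to gain.

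Several stronger readings are tempting and are not supported:
- **A fixed loss of 5 to 14 points.** The documents contain nothing that fixes a number. A figure of 14 appears only at rho 0.5 on normal data, measured against a parametric ANCOVA assumed to have 80% power at two-sided 0.05. That is not the remedy proposed here.
- **Baseline is ignored.** It is subtracted or divided out; only the covariate adjustment is missing.
- **The test is invalid or biased.** The rank sum test is valid under randomisation.
- **Sections 8.3.2 and 8.3.3 contradict each other.** They concern different endpoints and may use different methods.

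**What to change.** In section 8.3.3, replace the Wilcoxon test with a stratified rank ANCOVA:
1. Within each randomisation stratum (UDCA by bilirubin), rank the change from baseline and rank the baseline value. Do the same separately for percentage change.
2. Regress the outcome ranks on the baseline ranks within stratum and take residuals.
3. Compare the arms on the residuals with a CMH mean-score test over strata.

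Name change, not the follow-up value, as the ranked outcome: in simulation on normal data at rho 0.9, ranking follow-up lost power (73% against 77% for the planned test). State a rule for pooling sparse strata in the section 8.7 subgroups. Keep the Hodges-Lehmann estimate and its interval, labelled as an unadjusted description, because it will no longer correspond to the test.

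The cost is a paragraph of SAP text and a short program. Baseline values and strata are already held. The change should be made before database lock, since section 1 of the SAP classes analyses added after that as post hoc.
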